1 PROTOCOL SUMMARY

1.1 Synopsis

Short Title:

A Randomised Controlled Clinical Study to Evaluate the Efficacy of a Dentifrice in the Relief of Dentinal Hypersensitivity in a Chinese Population.

Background and Rationale:

The Chinese Ministry of Health (MoH) guidelines ([Ministry of Health China, 2010](#)) stipulate that two clinical studies are required to support the efficacy of a functional toothpaste, with at least one of these studies (for each claimed benefit) to be conducted on a local Chinese population.

To support long-term dentinal hypersensitivity (DH) relief claims of 0.454% stannous fluoride (SnF_2) containing toothpastes in China, a clinical study is required to be conducted in a local Chinese population.

Objectives and Endpoints:

Objective(s)	Endpoint(s)
Primary	
To compare the clinical efficacy of a 0.454% w/w SnF_2 dentifrice for the relief of DH, as elicited by an evaporative air stimulus (with Schiff sensitivity score), against a negative control dentifrice, when used twice daily for 8 weeks.	Change from Baseline in Schiff sensitivity score at 8 weeks.
Secondary	
To compare the clinical efficacy of a 0.454% w/w SnF_2 dentifrice for the relief of DH, as elicited by a tactile stimulus (yeaple probe), against a negative control dentifrice, when used twice daily for 8 weeks.	Change from Baseline in tactile threshold at 4 and 8 weeks.
To compare the clinical efficacy of a 0.454% w/w SnF_2 dentifrice for the relief of DH, as elicited by an evaporative air stimulus (with Schiff sensitivity score),	Change from Baseline in Schiff sensitivity score at 4 weeks.

Property of GSK Consumer Healthcare - Confidential

May not be used, divulged, published or otherwise disclosed without the consent of GSKCH

SOP-208661 Clinical Protocol Template v6.0

Page 10 of 85

against a negative control dentifrice, when used twice daily for 4 weeks.	
To compare the clinical efficacy of a positive control dentifrice for the relief of DH, as elicited by an evaporative air stimulus (with Schiff sensitivity score) and a tactile stimulus (yeaple probe), against a negative control dentifrice, when used twice daily for 8 weeks.	Change from Baseline in Schiff sensitivity score and tactile threshold at 4 and 8 weeks.
Safety	
To evaluate the safety and oral tolerability of the test dentifrices when used twice daily for 8 weeks.	Adverse Events
Exploratory	
To characterise Oral Health Related Quality of Life (OHRQoL) as measured by the short-form of the Dentine Hypersensitivity Experience Questionnaire (DHEQ-15) after 8 weeks treatment with a 0.454% w/w SnF ₂ dentifrice compared to a negative control dentifrice.	
At 8 weeks, change from Baseline in:
 
 • responses to Questions 7-9, DHEQ Section 1 • Total Score, Questions 1-15, DHEQ Section 2 • Restrictions, Adaptation, Social Impact, Emotional Impact & Identity Domains
To characterise OHRQoL as measured by the short-form of the DHEQ-15 after 8 weeks treatment with a positive control dentifrice compared to a negative control dentifrice.	
At 8 weeks, change from Baseline in:
 
 • responses to Questions 7-9, DHEQ Section 1 • Total Score, Questions 1-15, DHEQ Section 2 • Restrictions, Adaptation, Social Impact, Emotional Impact & Identity Domains

Study Design:

This will be a single centre, randomised, controlled, examiner-blind, 3 treatment arm, parallel group design study, stratified by maximum baseline Schiff sensitivity score (of the 2 selected 'test teeth'), with a treatment period of 8 weeks, to investigate the clinical efficacy of a SnF₂

Property of GSK Consumer Healthcare - Confidential

May not be used, divulged, published or otherwise disclosed without the consent of GSKCH

SOP-208661 Clinical Protocol Template v6.0

dentifrice in the reduction of DH in a Chinese population. The SnF₂ test dentifrice will be compared to commercialised negative and positive control dentifrices.

Study Products:

Investigational Product	Test Product	Reference Product (Negative Control)	Reference Product (Positive Control)
Product Name	Sensodyne Sensitivity & Gum (Chrysanthemum); Chinese commercialised dentifrice containing 0.454% SnF ₂ .	Crest Cavity Protection Fresh Lime (1150ppm fluoride as NaF); Chinese commercialised daily fluoride dentifrice.	Sensodyne Repair and Protect; Chinese commercialised dentifrice containing 5.0% w/w calcium sodium phosphosilicate.
Product Master Formulation Code (MFC)	Commercial Product CCI [REDACTED]	Commercial Product	Commercial Product CCI [REDACTED]
Usage Instructions	Apply a full ribbon of toothpaste on the head of the toothbrush provided. Brush teeth for 1*-timed minute, followed by brushing of the qualifying sensitive teeth. Following brushing rinse once with 10 ml of water from the rinsing cup provided.	Apply a full ribbon of toothpaste on the head of the toothbrush provided; brush teeth for 1*-timed minute. Following brushing rinse once with 10 ml of water from the rinsing cup provided.	Apply a full ribbon of toothpaste on the head of the toothbrush provided; brush teeth for 1*-timed minute. Following brushing rinse once with 10 ml of water from the rinsing cup provided.

*Following toothbrushing and/or rinsing subjects may also conduct a discretionary tongue clean using the provided toothbrush, but this is not a study requirement.

Type and Planned Number of Subjects:

A sufficient number of subjects will be screened to randomise approximately 195 subjects to ensure approximately 180 subjects (approximately 60 per treatment group) complete the study, allowing for dropouts.

Statistical Analysis Summary:

The primary efficacy variable is the change from baseline in Schiff score at 8 weeks. The primary comparison is between the test product and the negative control.

The secondary efficacy variables with corresponding comparisons are as follows:

Property of GSK Consumer Healthcare - Confidential

May not be used, divulged, published or otherwise disclosed without the consent of GSKCH

SOP-208661 Clinical Protocol Template v6.0

- Change from baseline in tactile threshold at 4 and 8 weeks; “test product versus negative control” and “positive control versus negative control”.
- Change from baseline in Schiff sensitivity score at 4 weeks; “test product versus negative control” and “positive control versus negative control”.
- Change from baseline in Schiff sensitivity score 8 weeks; “positive control versus negative control”.

The change from baseline in Schiff sensitivity score will be analysed using analysis of covariance (ANCOVA) with treatment as a factor and baseline Schiff sensitivity score as a covariate. Note that since the baseline Schiff sensitivity score will be included as a covariate, the baseline Schiff stratification value will not be included in the model.

Tactile is analysed in the same way with the addition of a factor for baseline Schiff stratification.

Table 1-1 Schedule of Activities

The schedule of activities table provides an overview of the subject visits and study procedures. The investigator may schedule visits (unplanned visits) in addition to those listed on the schedule of activities, to conduct evaluations or assessments required to protect the well-being of the subject.

Procedure/ Assessment	Screening	Study Period		
	Visit 1	Baseline Visit 2 Day 1 (Up to 28 days after Visit 1)	Visit 3 Day 29±3	Visit 4 Day 57±3
Informed consent	X			
Review of Subjects Oral Care Products to Confirm They Don't Contain any Anti-sensitivity Ingredients	X			
Review of Subjects Brushing Habits	X			
Demographics, Ethnicity	X			
Medical History and Prior Medication/Treatment	X			
Concomitant Medications		X	X	X
Full OST Examination	X	X	X	X
Full OHT Examination	X			X
Eligible Teeth Assessments (Dentition Exclusions, EAR, MGI, Tooth Mobility)	X			
Qualifying Tactile Assessment (Yeaple Probe) ¹	X			
Qualifying Evaporative Air Sensitivity (Schiff Sensitivity Score) ¹	X			
Identify Test Teeth	X			
Inclusion/Exclusion Criteria	X			
Subject Eligibility	X			
Dispense Acclimatisation Dentifrice, Toothbrush, Rinsing Cups, Diary and Timer ²	X			
Supervised Brushing with Acclimatisation Dentifrice ³	X			
Subject Adherence and Continuance		X	X	X
Subject completion of DHEQ-15		X		X
Tactile Assessment (Yeaple Probe) ⁴		X	X	X
Evaporative Air Assessment (Schiff Sensitivity Score) ⁵		X	X	X
Confirm Test Teeth ⁶		X		
Stratification and Randomisation		X		
Dispense Randomised Dentifrice, Toothbrush, Rinsing Cups and Diary		X		

ACCLIMATISATION PERIOD 14 TO 28 DAYS

Property of GSK Consumer Healthcare - Confidential

May not be used, divulged, published or otherwise disclosed without the consent of GSKCH

SOP-208661 Clinical Protocol Template v6.0

Supervised Brushing with Allocated Dentifrice and Reminder of Product Usage Instructions ⁷			X	X	
Subjects Bring Study Supplies and Diary to Site			X	X	X
Weight Check of Returned Study Dentifrice and Subject Brushing Video's, and Compliance Discussion ⁷			X	X	X
Adverse Events ⁸	X		X	X	X
Study Conclusion					X

Abbreviations: OST = Oral Soft Tissue; OHT = Oral Hard Tissue; EAR = Erosion, Abrasion, Recession; MGI = Modified Gingival Index; ; SnF₂ = stannous fluoride; DHEQ = Dentine Hypersensitivity Experience Questionnaire.

Footnotes:

¹ Qualifying Schiff sensitivity and tactile threshold scores will be recorded in the case report form (CRF). Evaporative air assessment to follow tactile assessment; minimum 5 minutes time lapse between the two assessment types for tooth recovery. At Screening, maximum force for tactile = 20g.

² Subject is instructed to bring all supplies back to next visit.

³ Study supplies to be returned to subject (for use at home) after supervised brushing.

⁴ At Baseline, maximum force = 20g, at all subsequent visits maximum force = 80g.

⁵ Evaporative air assessment to follow tactile assessment; minimum 5 minutes time lapse between the two assessment types for tooth recovery.

⁶ Subject's with 'test teeth' that don't respond to tactile and/or Schiff at Baseline, may be required to have all eligible teeth identified at Screening re-assessed to identify 'test teeth'. A minimum of 5 minutes time lapse will be required between assessments.

⁷ Subject is instructed to bring all supplies back to subsequent visits for compliance checks. Study supplies to be returned to subject after supervised brushing. Subject is re-dispensed a new toothbrush at Visit 3.

⁸ Adverse Events (AEs) and therefore all Serious Adverse Events (SAEs) will be collected immediately after a subject provides consent to participate in the study by the completion of the informed consent form (ICF).

2 INTRODUCTION

Dentine hypersensitivity (DH) has been defined as ‘pain derived from exposed dentine in response to chemical, thermal, tactile, or osmotic stimuli which can’t be explained as arising from any other dental defect or disease’ ([Addy, 1985](#); [Canadian Advisory Board on Dentin Hypersensitivity, 2003](#)). The primary aetiological factors associated with the onset of DH include gingival recession and/or enamel loss (e.g. through erosion or abrasion) that result in exposure of dentine with patent dentinal tubules ([Orchardson, 2000](#)). The hydrodynamic theory of DH hypothesises that a stimulus external to the tooth (e.g. a temperature/osmotic differential) causes transport of the fluid resident within dentinal tubules ([Brännström, 1962](#)). This fluid movement may stimulate nerve processes in the pulpal area of the dentine including irritation of odontoblasts, pulpal neurons, and even subodontoblastic blood vessels ([Hall, 2000](#)), resulting in the characteristic short, sharp pain of DH.

Currently there are two approaches to the management of DH: either nerve depolarisation or dentinal tubule occlusion. Nerve depolarising agents, typically potassium salts, generally require a period of use (for example, 14 to 28 days) before their benefit is established. The delivery of potassium ions to the dentine-pulp junction (odontoblastic layer) *via* dentinal tubules is believed to result in depolarisation of the afferent nerve membrane thereby interrupt the pain response ([Orchardson, 2000](#)). The second approach uses tubule occluding agents which physically block the exposed end of the dentinal tubules, thus reducing dentinal fluid movement and pulpal irritation. Tubule occluding agents, like stannous salts, serve to seal or block the dentine tubules and thereby reduce the effect of external stimuli. Such agents are believed to function by precipitating insoluble materials onto the dentine surface and/or within the dentinal tubules to reduce dentinal fluid transport ([Pashley, 1986](#)).

Stannous fluoride (SnF_2) has been incorporated into oral hygiene products indicated for the reduction of DH since the 1960’s ([Schiff, 2006](#)). SnF_2 provides relief from DH by the occlusion of the dentinal tubules through chemical precipitation of stannous oxides and hydroxides onto the surface of the dentine. Proctor and Gamble (P&G) and GlaxoSmithKline Consumer Healthcare (GSK CH) have marketed SnF_2 -containing dentifrices indicated for DH relief, with published evidence demonstrating longitudinal clinical efficacy ([Ni, 2010](#); [Parkinson, 2011](#); [Makin, 2013](#)).

2.1 Study Rationale and Background

The Chinese Ministry of Health (MoH) guidelines ([Ministry of Health China, 2010](#)) stipulate that two clinical studies are required to support the efficacy of a functional toothpaste, with at least one of these studies (for each claimed benefit) to be conducted on a local Chinese population.

To support DH efficacy claims GSK CH holds an extensive global clinical data package for 0.454% SnF_2 dentifrices ([Creeth et al, 2019](#); [Goyal et al, 2017](#); [Parkinson et al, 2013](#); [Parkinson](#)

Property of GSK Consumer Healthcare - Confidential

May not be used, divulged, published or otherwise disclosed without the consent of GSKCH

SOP-208661 Clinical Protocol Template v6.0

Page 16 of 85

[et al, 2015; Parkinson et al, 2016;](#)). To support long-term dentine hypersensitivity claims in China, two further DH clinical studies have been conducted.

The first DH study ([GSK CH Clinical Study 205794, 2017](#)) met the primary objective (Schiff sensitivity score, at both 4 and 8 weeks), but did not meet the secondary objective (tactile threshold). A further clinical study was conducted ([Tao, 2020](#)), which demonstrated significantly reduced dentine hypersensitivity from baseline for the SnF₂ dentifrice, however, there was no between treatment differences when compared to a negative and positive control.

To support long-term DH relief claims of 0.454% SnF₂ containing toothpastes in China, a clinical study is required to be conducted in the local Chinese population.

2.2 Benefit/Risk Assessment

Complete information for the acclimatization and study products may be found on the product labels.

2.3 Mechanism of Action/Indication

SnF₂ is a dentine tubule occluding agent that is being investigated in subjects with DH. Such agents have been shown to function by precipitating insoluble materials onto the dentine surface and/or within the dentinal tubules to reduce dentinal fluid transport ([Parkinson 2011; Parkinson 2013](#)).

3 STUDY OBJECTIVES AND ENDPOINTS

Objective(s)	Endpoint(s)
Primary	
To compare the clinical efficacy of a 0.454% w/w SnF ₂ dentifrice for the relief of DH, as elicited by an evaporative air stimulus (with Schiff sensitivity score), against a negative control dentifrice, when used twice daily for 8 weeks.	Change from Baseline in Schiff sensitivity score at 8 weeks.
Secondary	
To compare the clinical efficacy of a 0.454% w/w SnF ₂ dentifrice for the relief of DH, as elicited by a tactile stimulus (yeaple probe), against a negative control dentifrice, when used twice daily for 8 weeks.	Change from Baseline in tactile threshold at 4 and 8 weeks.

Property of GSK Consumer Healthcare - Confidential

May not be used, divulged, published or otherwise disclosed without the consent of GSKCH

SOP-208661 Clinical Protocol Template v6.0

Page 17 of 85

To compare the clinical efficacy of a 0.454% w/w SnF ₂ dentifrice for the relief of DH, as elicited by an evaporative air stimulus (with Schiff sensitivity score), against a negative control dentifrice, when used twice daily for 4 weeks.	Change from Baseline in Schiff sensitivity score at 4 weeks.
To compare the clinical efficacy of a positive control dentifrice for the relief of DH, as elicited by an evaporative air stimulus (with Schiff sensitivity score) and a tactile stimulus (yeaple probe), against a negative control dentifrice, when used twice daily for 8 weeks.	Change from Baseline in Schiff sensitivity score and tactile threshold at 4 and 8 weeks.
Safety	
To evaluate the safety and oral tolerability of the test dentifrices when used twice daily for 8 weeks.	Adverse Events
Exploratory	
To characterise Oral Health Related Quality of Life (OHRQoL) as measured by the short-form of the Dentine Hypersensitivity Experience Questionnaire (DHEQ-15) after 8 weeks treatment with a 0.454% w/w SnF ₂ dentifrice compared to a negative control dentifrice.	
At 8 weeks, change from Baseline in:
 
 • responses to Questions 7-9, DHEQ Section 1 • Total Score, Questions 1-15, DHEQ Section 2 • Restrictions, Adaptation, Social Impact, Emotional Impact & Identity Domains
To characterise OHRQoL as measured by the short-form of the DHEQ-15 after 8 weeks treatment with a positive control dentifrice compared to a negative control dentifrice.	
At 8 weeks, change from Baseline in:
 
 • responses to Questions 7-9, DHEQ Section 1 • Total Score, Questions 1-15, DHEQ Section 2 • Restrictions, Adaptation, Social Impact, Emotional Impact & Identity Domains

This study will be considered successful if there is a statistically significant difference in the primary efficacy variable, change from baseline in Schiff sensitivity score and a between treatment difference in favour of the SnF₂ dentifrice compared to the negative control, after 8 weeks of treatment. The size of the effect is important to meet Chinese MoH guidelines, a 15% difference between the SnF₂ dentifrice and the negative control must be observed.

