To monitor subject adherence to the product usage instructions, subjects will be asked to record 2 brushing occasions per week using their smartphone video. Every 2 weeks a designated member of the clinical study team will review these videos and confirm compliance with product usage instructions in the case report form (CRF). These video's will not be considered to be source data. Subjects confirmed as non-compliant (Eg. subjects who don't correctly follow the product use instructions) will be reminded about the product usage instructions and documented as a protocol deviation. A check-list will be provided to the clinical study site so that they correctly understand what is considered to be compliant with the product usage instructions.

In line with published recommendations ([Holland, 1997](#)) and the requirement of Chinese Ministry of Health guidelines ([Ministry of Health \(China\), 2010](#)) for the testing of functional dentifrices (desensitising), two independent stimulus-based efficacy measures will be employed (tactile and evaporative air sensitivity) to evaluate the DH efficacy of the experimental dentifrice. A tactile stimulus will be administered using a constant pressure probe (yeaple probe ([Polson, 1980](#))). An evaporative (air) stimulus will be administered using a dental air syringe. Response to this stimulus will be evaluated using the Schiff sensitivity scale ([Schiff, 1994](#)). In accordance with the MoH guidelines, the mean values of each index should decrease during the clinical trial, and have statistical significance compared with the control group. When one of the mean values of the indices decreases by 15% or more than 15%, then the trial group can be considered to have DH efficacy ([Ministry of Health China, 2010](#)).

Property of GSK Consumer Healthcare - Confidential

May not be used, divulged, published or otherwise disclosed without the consent of GSKCH

SOP-208661 Clinical Protocol Template v6.0

A qualifying response to a tactile stimulus followed by a qualifying air blast on all teeth qualifying for tactile will be included in this study. At Screening and Baseline subjects will have a minimum of two teeth with a tactile score of ≤ 20 g and Schiff sensitivity score of ≥ 2 . To ensure consistent responders are entered into the study, the 2 'test teeth' must be selected from those teeth eligible for both Schiff and tactile at Screening, and confirmed at Baseline.

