12.3.1 Primary Analysis(es)

The primary efficacy variable is the change from baseline in Schiff score at 8 weeks. The primary comparison is between the test product and the negative control. As there is only a single primary objective no adjustment for multiple comparisons is required.

The Schiff sensitivity score is derived as the average score of the 2 test teeth. The change from baseline is derived from the individual teeth first before calculating the average change of the 2 test teeth.

A summary of the Schiff sensitivity score and change from baseline will be provided by treatment group and time.

The change from baseline in Schiff sensitivity score will be analysed using analysis of covariance (ANCOVA) with treatment as a factor and baseline Schiff sensitivity score as a covariate. Note that since the baseline Schiff sensitivity score will be included as a covariate, the baseline Schiff stratification value will not be included in the model.

The assumption of normality and homogeneity of variance in the ANCOVA model will be investigated. In case of violation of these assumptions a suitable transformation or a non-parametric method eg the van Elteren test, adjusting for the maximum baseline Schiff Sensitivity scores will be performed and results will be compared with the ANCOVA results.

If the inferences from the two analyses are similar then both sets of results will be reported and emphasis will be made on the ANCOVA results. In case of discrepancies between p-values of ANCOVA and non-parametric method, inferences will be drawn on the nonparametric analyses. Ultimately inferences will be drawn on the size of difference rather than just the p-value and it is hoped to see a difference of >15% between treatment groups. This difference is based on the adjusted Test and Control means for the change from baseline: $100 \times [\text{Adjusted Mean Difference} / \text{Adjusted Mean of Negative Control}]$. This percentage difference will be reported and tabulated along with the change from baseline results.

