12.3.2 Secondary Analyses

The secondary efficacy variables with corresponding comparisons are as follows:

- Change from baseline in tactile threshold at 4 and 8 weeks; “test product versus negative control” and “positive control versus negative control”.

Property of GSK Consumer Healthcare - Confidential

May not be used, divulged, published or otherwise disclosed without the consent of GSKCH

SOP-208661 Clinical Protocol Template v6.0

- Change from baseline in Schiff sensitivity score at 4 weeks; “test product versus negative control” and “positive control versus negative control”.
- Change from baseline in Schiff sensitivity score 8 weeks; “positive control versus negative control”.

Tactile score including the change is derived in the same manner as for the Schiff score.

A summary of the secondary variables and change from baseline will be provided by treatment group and time.

Change from baseline in Schiff will be analysed as per the primary variable. Change from baseline in Tactile variables will be analysed using ANCOVA with treatment as a factor and baseline Schiff sensitivity score as a covariate.

The assumption of normality and homogeneity of variance in ANCOVA model will be assessed as described for the primary efficacy analysis.

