To characterize OHRQoL as measured by the short-form of the DHEQ-15 after 8 weeks treatment with a positive control dentifrice compared to a negative control dentifrice.	
At 8 weeks, change from Baseline in:
 
 • responses to Questions 7-9, DHEQ Section 1 • Total Score, Questions 1-15, DHEQ Section 2 • Restrictions, Adaptation, Social Impact, Emotional Impact and Identity Domains

This study will be considered successful if there is a statistically significant difference in the primary efficacy variable, change from baseline in Schiff sensitivity score and a between treatment difference in favor of the SnF₂ dentifrice compared to the negative control, after 8 weeks of treatment. The size of the effect is important to meet Chinese MoH guidelines, a 15% difference between the SnF₂ dentifrice and the negative control must be observed.

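### The 15% effect-size condition is mandatory in Protocol 3 and SAP 1.2, hoped for in Protocol 12.3.1 and absent from the SAP's primary analysis, so a significant Schiff result below 15% can be read as success or failure

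*Protocol*

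**What the plan says.** - **Protocol 3, success sentence.** "This study will be considered successful if there is a statistically significant difference in the primary efficacy variable, change from baseline in Schiff sensitivity score", with the difference favouring SnF₂ over the negative control at 8 weeks. No percentage appears in this sentence.
- **Protocol 3, next sentence.** Citing the Chinese guideline, it adds that "a 15% difference between the SnF₂ dentifrice and the negative control must be observed". SAP 1.2 repeats the requirement ("and the negative control must be observed").
- **Protocol 12.3.1.** "Ultimately inferences will be drawn on the size of difference rather than just the p-value", and in the same sentence "it is hoped to see a difference of >15% between treatment groups". It then defines the quantity ("This difference is based on the adjusted Test and Control means for the change from baseline") as 100 × adjusted mean difference / adjusted mean change of the negative control, and commits to tabulating it.
- **Protocol 4.2.** The guideline is reported in two parts. Each index should decrease and differ significantly from control. On size: "When one of the mean values of the indices decreases by 15% or more than 15%, then the trial group can be considered" to show efficacy.
- **Protocol 12.3.2.** "Tactile score including the change is derived in the same manner as for the Schiff score". A percentage difference for tactile is not mentioned.
- **SAP 4.4.1.2.** It specifies adjusted means, confidence intervals, differences and p-values at the two-sided 5% level. It has no 15% rule and no percentage difference. SAP Table 5-1 does not record either omission as a change.

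**The concern.** One threshold is described with three different properties:

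- **Status:** mandatory in Protocol 3 and SAP 1.2, an aspiration in 12.3.1, absent from SAP 4.4.1.2.
- **Scope:** the primary Schiff comparison in Protocol 3 and 12.3.1, either index in 4.2.
- **Boundary:** 15% in Protocol 3, 15% or more in 4.2, more than 15% in 12.3.1.

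No passage ranks or reconciles these. Suppose Schiff is significant at 12% and tactile is significant at 20%. The mandatory sentence in Protocol 3 is not met. Under 12.3.1 the result only falls short of a hope. Under 4.2 the size condition is met through tactile, but the visible text plans no tactile percentage with which to show it.

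The trial is run to support a claim. If the standing of its size criterion is left open, the conclusion can be settled after the results are known.

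**Working it through.** **Inputs.** Protocol 12.1 and SAP 1.4: 60 evaluable subjects per group, difference 0.3, SD 0.501, two-sided 5% two-sample t-test, 90% power, and 0.3 described as roughly 15%. Protocol 12.3.1: the percentage formula. The negative control's mean change is not given, so a range is assumed.

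**1. The plan's own figure.** SE = 0.501 × √(2/60) = 0.0915. Power at a difference of 0.3 is 90.2% (noncentral t, 118 df) or 90.7% (normal approximation). The stated 90% reproduces. It is power for significance alone.

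**2. Smallest significant difference.** 1.980 × 0.0915 = 0.181.

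**3. When a significant result can fall below 15%.** Under the 12.3.1 formula, 15% corresponds to 0.15 × C, where C is the size of the negative control's mean change. A significant result below 15% is possible only if 0.15 × C > 0.181, that is, C > 0.181/0.15 = 1.21.

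**4. How likely that is at a true difference of 0.3.** The probability of significance is 1 − Φ((0.181 − 0.3)/0.0915) = 0.903. Subtracting the probability that the result is both significant and at least 0.15 × C gives the last column.

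| Assumed C | 15% equals | P(significant and ≥15%) | P(significant but <15%) |
|---|---|---|---|
| 0.5 | 0.075 | 0.903 | 0% |
| 1.0 | 0.150 | 0.903 | 0% |
| 1.5 | 0.225 | 0.794 | 11% |
| 2.0 | 0.300 | 0.500 | 40% |

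**5. The equivalence in Protocol 12.1.** Treating 0.3 as 15% implies a denominator of 0.3/0.15 = 2.0, which is the last row. The documents do not say what that denominator is.

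**6. If 15% is binding and equals 0.3.** Meeting both conditions has probability 0.50 at a true difference of 0.3. For a 90% chance of observing at least 0.3, the true difference would have to be about 0.3 + 1.282 × 0.0915 = 0.417.

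These figures treat C as fixed and use the unadjusted SD from the sample-size section. They are approximations to the ANCOVA result.

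**The case against.** The strongest reply is that Protocol 3 has two tiers: trial success is significance in favour of SnF₂, and the 15% is an extra condition for the guideline claim. The success sentence supports this, since it contains no percentage. A reader might infer that Protocol 3 plainly declares a significant result below 15% a failed trial, and the text does not go that far. But no passage states the two-tier reading either, the two sentences share one paragraph, and 12.3.1 rests inference on the size of the difference. The ambiguity stands.

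Second, 12.3.1 does more than hope, because it ties inference to size and commits to reporting the percentage. That is correct. It still sets no decision rule, and the SAP section that should carry the commitment forward does not.

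Third, 4.2 is design rationale and not a success rule. A reader might infer from it that one index alone is enough. It is not: each index must also be significant versus control. In addition, 4.2 speaks of a decrease in an index mean, which is not shown to be the same quantity as the ratio of changes in 12.3.1. Tactile benefit is also a rise in threshold, not a decrease. A figure for how much the either-index reading raises the chance of meeting 15% would need a tactile effect and a correlation that the documents do not supply.

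Fourth, 40% should not be quoted on its own. It needs a denominator of 2.0. Test teeth enter at Schiff 2 or 3, and Protocol 4.2 describes the negative control as without demonstrated efficacy, though the same section expects placebo and no-treatment effects. The 12% example likewise needs a control change of at least 0.181/0.12 = 1.51. This objection stands, and the range is what should be reported.

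Finally, the primary test is not loosened. Endpoint, comparison, model and the 5% level are fixed, and every reading of the 15% only adds to them.

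**Conclusion.** The inconsistency is real and lies in the current text of both documents. The status, scope and boundary of the 15% condition differ between sections. The SAP's primary analysis leaves out both the rule and the promised Schiff percentage without recording a change. A significant Schiff result below 15% can be read either way.

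At a true difference of 0.3, the chance of that result runs from 0% (control change up to about 1.21) through 11% (1.5) to 40% (2.0, or the 12.1 equivalence). The control change is an assumption throughout.

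A reader might infer an inflated false-positive rate on the primary comparison, or that the sections always give opposite verdicts. The documents support neither. What is unsettled is the conclusion to be drawn from one class of significant results. The SAP's list of displays is redacted, so the statements about missing percentages rest on the visible text only.

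**What to change.** Before unblinding, put one rule in identical words in Protocol 3 and 12.3.1 and in SAP 1.2 and 4.4.1.2, with one inequality (15% or more) and the 12.3.1 formula.

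- Because Protocol 3 makes the condition mandatory, replace the hoped-for clause in 12.3.1 with: success requires two-sided p<0.05 in favour of SnF₂ and an observed Schiff percentage difference of 15% or more at 8 weeks.
- If the sponsor intends 15% only as the guideline condition, say so explicitly and report it as a separate, prespecified conclusion.
- In either case, report the guideline condition as 4.2 gives it: each index significant versus control, and 15% or more on at least one.
- Add the Schiff percentage difference to SAP Table 14.2.2.1.2. Add the tactile percentage difference, signed so that a higher threshold counts as benefit, to Table 14.2.3.1.2.

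**Cost.** The edits are wording in four places and a row in each of two tables; no design change is needed. The substantive cost falls on the sponsor if 15% is made binding. The 90% power then no longer describes the chance of success, which is about 50% at a true difference of 0.3 when 0.3 equals 15%. Protocol 12.1 and SAP 1.4 should say so.
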